## 2 weeks post biopsy

- Record adverse skin reactions i.e seroma formation and cutaneous staining

## Follow-up phone call

- Record self-reported skin reactions

## Biopsy results

- Staining characteristics of each lymph node will be documented as blue, radioactive, or fluorescent (or a combination).

## **7.8. Long term follow-up assessments**

Not applicable.

## **7.9. Qualitative assessments**

Not applicable.

## **7.10. Withdrawal criteria**

Participants are free to withdraw at any time and are not obliged to give reason(s). The CI, PI or delegate will make a reasonable effort to ascertain the reason(s), both for those who express their right to withdraw and for those lost to follow up, while fully respecting the individual's rights.

The investigator may withdraw a patient at any time if it is in the best interest of the patient and treatment continuation would be detrimental to the patients' wellbeing. A full explanation will be provided. If the trial is being conducted on an intention to treat basis, and the participant has been randomised and given the intervention or standard care, they will be asked to complete trial visits as per the protocol, if the CI considers it appropriate, to allow for an intention to treat analysis - but will be censored in the per-protocol analysis. Participants are free to refuse to do so.

Those withdrawn, including those lost to follow-up, will be identified and a descriptive analysis of them provided, including the reasons for their loss, if known, and its relationship to treatment and outcome.

If a participant withdraws or is withdrawn, they will also have the right to withdraw their data and any research tissue collected. Data collected up to the point of withdrawal will be retained and used for analysis unless a participant expresses their right to withdraw their data.

## **7.11. Storage and analysis of clinical samples**

No research samples will be collected during the trial.

## **7.12. End of trial**

The end of trial at all Sites is defined as last participant last visit. The last visit for each participant will be at the 3-month follow-up phone call. The Sponsor and CI have the right at any time to terminate the trial for clinical or administrative reasons.

The end of the trial will be reported to the Sponsor, REC and NHS R&D Office(s) within 90 days, or 15 days if the trial is terminated prematurely. The CI will ensure that any appropriate follow up is arranged for all participants.

A final clinical trial report will be submitted to the REC and Sponsor within 1 year of the end of the trial.

## **8. TRIAL TREATMENTS**

### **8.1. Name and description of trial treatments**

Participants in each Cohort will be randomised to ICG plus additional tracer (standard care) or ICG alone (intervention).

After randomisation, participants in Cohort 1 will undergo either routine radiocolloid injection 2 hours prior to surgery followed by an injection of 2ml of 0.5% ICG (intra-dermal/subareolar) at the time of surgery (standard care) or an injection of 2ml of 0.5% ICG alone (intra-dermal/subareolar) (intervention). The breast will be massaged for 2 minutes before measuring levels of radioactivity in the breast and axilla with a gamma probe and detection of nodes using the fluorescence PDE camera.

Participants in Cohort 2 will either be injected with 2mls of 2.5% Patent Blue dye followed by an additional 2mls 0.5% ICG (standard care) yielding a total injectate volume (blue dye/ICG) of 3mls or 2mls 0.5% ICG alone (intervention). The fluorescence PDE camera will then be used to observe the subcutaneous lymphatic streams with fluorescent imaging.

Following surgical dissection and excision, staining characteristics of each lymph node will be documented as blue, radioactive, or fluorescent (or combination thereof). The gamma probe and fluorescence PDE camera will be used to check for absence of any residual activity or fluorescence within the axilla. The time from incision to completion of node excision will be recorded in minutes.

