### 3.1. Primary objective

To determine the sensitivity of ICG fluorescence imaging alone for SLN detection compared to a combination of ICG and standard tracer.

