#### Cohort 2 (Dundee)

1. ICG 2mls 0.5%
2. ICG 2mls 0.5% combined with Patent Blue dye 2mls 2.5%

Patients will continue with standard care for further treatment of their condition.

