### **8.2. Name and description of intervention and standard care**

- Radioisotope Technetium^99 nanocolloid, 20 MBq
- Patent Blue dye 2.5%
- Indocyanine green (ICG) 0.5%

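### In Section 8.1 the Cohort 2 standard-care components add up to 4 ml, but the same sentence gives a total of 3 ml

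*Protocol*

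**What the plan says.** Section 8.1 of the Protocol gives the instruction for Cohort 2. Standard-care participants receive "2mls of 2.5% Patent Blue dye followed by an additional 2mls 0.5% ICG (standard care) yielding a total injectate volume (blue dye/ICG) of 3mls". The comparator in that sentence, the intervention arm, is 2 ml of 0.5% ICG with no second tracer.

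Section 4, under Cohort 2 (Dundee), lists the standard-care arm as "ICG 2mls 0.5% combined with Patent Blue dye 2mls 2.5" per cent, with no total. Section 8.2 lists tracer strengths and, for Patent Blue and ICG, no volumes.

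For Cohort 1, Sections 4 and 8.1 both give 2 ml of 0.5% ICG in each arm and state no total volume, so the same problem does not arise there.

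These volumes define the arms compared under the primary objective in Section 3.1: "To determine the sensitivity of ICG fluorescence imaging alone for SLN detection compared to a combination of ICG and standard tracer".

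**The concern.** The sentence in Section 8.1 tells staff what to inject, and it contradicts itself. The ICG is described as additional to the dye, so the two volumes add. The bracket after the total names both dye and ICG, so the total covers both. At least one of the three figures (dye volume, ICG volume, total) must be wrong, or some step that explains the missing 1 ml has been left out.

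The consequence depends on which figure is wrong:

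- If it is the total, the error is editorial and the arms are as Section 4 describes.
- If it is the ICG volume, the Cohort 2 arms differ in the amount of ICG as well as in the presence of dye. The comparison would then no longer isolate the effect of adding blue dye.
- If it is the dye volume, the ICG comparison is intact but dye exposure is not what Sections 4 and 8.1 state. That bears on cutaneous staining, an outcome in Section 3.6, and on the recording of nodes as blue.

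Section 9.2.2 analyses each cohort separately, so Cohort 1 cannot make up for a problem in Cohort 2. The sentence governs all 25 participants planned for the Cohort 2 standard-care arm (Section 4). Section 12.5 allows no waivers and requires breaches to be recorded. With contradictory volumes, it is unclear what would count as compliance.

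**Working it through.** **Inputs**

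- Patent Blue, Cohort 2 standard care: 2 ml of 2.5% (Sections 4 and 8.1).
- ICG, Cohort 2 standard care: 2 ml of 0.5% (Sections 4 and 8.1).
- Stated total, Cohort 2 standard care: 3 ml (Section 8.1 only).
- ICG, Cohort 2 intervention: 2 ml of 0.5% (Sections 4 and 8.1).

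**Step 1: try to reproduce the stated total.**

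Total = dye volume + ICG volume = 2 + 2 = 4 ml. The protocol says 3 ml, so its figure is not reproduced. The difference is 4 − 3 = 1 ml, which is 1/4 = 25% of the summed volume, or 1/3 = 33% of the stated total.

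**Step 2: look for an explanation.**

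Section 4 repeats 2 ml of each. Section 8.2 gives no volumes for these two tracers. The protocol mentions no dilution, discarded portion or partial injection that would turn 4 ml into 3 ml. The sentence in Section 8.1 is complete, with no gap or redaction, so a text-extraction fault does not account for it.

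**Step 3: work through the possible readings.**

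The ICG ratio is the ICG volume in standard care divided by the 2 ml in the ICG-alone arm. The dye ratio is the dye volume divided by the stated 2 ml. ICG strength is 0.5% in both arms, so the volume ratio is also the ratio of amounts.

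| Reading | Dye (ml) | ICG (ml) | Total (ml) | ICG ratio | Dye ratio |
|---|---|---|---|---|---|
| Total is wrong | 2 | 2 | 4 | 2/2 = 1.0 | 2/2 = 1.0 |
| Dye volume is wrong | 1 | 2 | 3 | 2/2 = 1.0 | 1/2 = 0.5 |
| Both components are wrong, equally | 1.5 | 1.5 | 3 | 1.5/2 = 0.75 | 1.5/2 = 0.75 |
| ICG volume is wrong | 2 | 1 | 3 | 1/2 = 0.5 | 2/2 = 1.0 |

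**Step 4: state the range.**

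If 3 ml is right and neither component exceeds its stated 2 ml, then ICG = 3 − dye, which lies between 3 − 2 = 1 ml and 2 ml. The ICG ratio therefore lies between 0.5 and 1.0. It is 1.0 in two of the four readings shown. The readings are not equally likely in any known sense; the table shows only what each would imply.

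**The case against.** The strongest reply is that the protocol is consistent on the quantity that matters most. Wherever an ICG volume is given, in both arms of both cohorts, it is 2 ml of 0.5%. No section mentions 1 ml or 1.5 ml of ICG. The 3 ml appears once and is presented as a result of the components, not as a separate instruction. On this view the arms are specified with equal ICG and one derived figure is discordant. That stands in so far as the document never states unequal ICG. It does not settle which figure is wrong, and it leaves the contradiction in place.

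A second reply is that little in the statistics depends on this. Section 9.1 describes a pilot with no power calculation, Section 9.2.2 calls all analysis exploratory, and no sample size, error rate or stopping rule uses the 3 ml. That also stands. The reason to correct the text is that a treatment instruction cannot be followed as written.

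Two stronger readings are tempting. A reader might infer that the Cohort 2 comparison is confounded because standard care receives half the ICG. That is the lowest of the possible ratios and requires the whole 1 ml to fall on ICG, which no passage says. Nor does the document show how such a difference would change sentinel node identification. A reader might also infer that different surgeons will follow different figures. Cohort 2 is a single site (Section 4), and eligibility requires a biopsy planned under local standard care with ICG plus Patent Blue (Section 6.1). Misreading remains possible, but nothing shows divergent practice.

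**Conclusion.** The contradiction is real and lies within one sentence: components of 4 ml against a total of 3 ml, with 1 ml unexplained. It affects the treatment specification for the 25 planned Cohort 2 standard-care participants and does not touch Cohort 1.

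The document does not establish that ICG exposure differs between the Cohort 2 arms. It leaves a doubt, which comes only from the total. The ICG ratio of 0.5 to 1.0 assumes that the ICG-alone arm receives its stated 2 ml and that neither standard-care component exceeds its stated 2 ml. Dye exposure could likewise be as stated or as low as half of that. Any effect on detection rates or skin staining cannot be quantified from the document.

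The point deserves correction because it concerns what is injected, the document cannot resolve it, and putting it right is cheap.

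**What to change.** The sponsor and clinical lead should reconcile Section 4 (Cohort 2) with Section 8.1 so that the two component volumes and the total agree. If a preparation step explains the 3 ml, it should be described. The same correction should state whether the amount of ICG is identical in the two Cohort 2 arms. Which figure is right is for them to determine.

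If the ICG amount proves to be the same in both arms, nothing in the analysis needs to change. If it differs, Section 9.2.2 should say that the Cohort 2 comparison includes a difference in ICG as well as the addition of blue dye.

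Recording the volume of each tracer actually given would be a useful option. Section 8.5 already has tracer use entered in the CRF, so this would add two fields, but the correction does not depend on it.

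The cost is a one-line change to the protocol, submitted through the amendment route in Section 12.10.

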**VII. KEY WORDS: fluorescence, sentinel lymph node (SLN), breast cancer**

**VIII. TRIAL FLOW CHART**

## 1. BACKGROUND

Fluorescence navigation using the fluorochrome ICG has been employed to visualise lymphatic channels and nodal tissue for identification of SLN(s) in breast and other site cancers. The fluorescent signal is captured by a photodynamic eye composed of a series of light emitting diodes (LEDs) that produce light at a wavelength of 760nm, a lens and a filter. The detector is a charge coupled device camera that filters out wavelengths below 820nm. The fluorescent signals appear on a TV monitor. Fluorescence develops immediately following intra-dermal/subareolar injection of ICG and within seconds can be seen in the subcutaneous vessels of the breast. The illuminated subcutaneous lymphatic channels can be visualised on the Photo Dynamic Eye (PDE) display and progression of the ICG within the lymphatic system tracked as it passes towards the axilla. The fluorescence is scattered by superficial tissues and cannot be detected at a depth of more than 1cm with current technology. The fluorescent signal is lost from scattering and technical improvements are aimed at reducing scatter and improving sensitivity (e.g. development of a PDE which can detect fluorescence at a depth of up to 2cm). Pressure applied to the axillary region enables lymph nodes to be visualised percutaneously before the skin incision is made. The fluorescent lymphatic channels disappear around the level of the lower axilla and can otherwise only be detected (together with sentinel nodes) after the skin incision has been made. This point at which the subcutaneous lymphatic channels cease to be seen is used to determine the site of skin incision. Application of pressure may permit visualisation of a sentinel node through the skin, but otherwise an incision is made at the point where the fluorescent lymphatics disappear.

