### 3.6. Table of endpoints/outcomes

Objectives	Outcome Measures	Timepoint(s) of evaluation of this outcome measure (if applicable)
Primary Objective To determine the sensitivity of fluorescence imaging alone for SLN identification compared with a combination of ICG and a standard tracer (blue dye or radioisotope)	Percentage of patients with successful identification of the SLN using ICG alone or combined with a standard tracer, stratified by cohort	At the time of SLN biopsy
Secondary Objectives Procedural node positivity rates	Proportion of SLN biopsy cases with tumour deposits in at least one node (including macrometastases, micrometastases and isolated tumour cells)	Post-surgery, when histopathology results are available
Adverse events from SLN biopsy	Seroma formation Cutaneous staining Other adverse reactions to tracers	2 weeks and 3 months

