## 15. APPENDICIES

### 15.1. Appendix 1 - Risk

Risks associated with trial interventions				
 A ≡ Comparable to the risk of standard medical care  B ≡ Somewhat higher than the risk of standard medical care  C ≡ Markedly higher than the risk of standard medical care				
Justification:				

Standard SLN detection techniques involve the use of blue dye or radioisotopes. ICG fluoresce detection is routinely used in combination with these standard techniques. Participants in this study will be in two cohorts. Participants in Cohort 1 will be randomised to either ICG alone (intervention) or ICG plus radioisotope (standard care). Participants in Cohort 2 will be randomised to ICG alone intervention) or ICG plus blue dye (standard care).
				
What are the key risks related to therapeutic interventions you plan to monitor in this trial?		How will these risks be minimised?		
Intervention	Body system/Hazard	Activity	Frequency	Comments
Possibility of the ICG alone not identifying SLN	Breast/axilla	Where no SLNs are identified by the ICG the surgeon will randomly sample axillary nodes. This is normal practice when this occurs during standard care.	At time of surgery	There is a small chance that this may cause an increase in seroma formation and the possibility of the development of lymphoedema
Outline any other processes that have been put in place to mitigate risks to participant safety (e.g. DMC, independent data review, etc.)				
None required				
Outline any processes (e.g. IMP labelling +/- accountability +/- trial specific temperature monitoring) that have been simplified based on the risk adapted approach.				
None required				

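### An ICG failure followed by random sampling could be recorded as an ICG success, because the only node-level tracer readout specified is documented after excision

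*Protocol*

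**What the plan says.** The primary outcome in protocol section 3.6 is "Percentage of patients with successful identification of the SLN using ICG alone or combined with a standard tracer, stratified by cohort", evaluated at the time of SLN biopsy. Successful identification is not defined further.

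On measurement, section 8.1 states: "Following surgical dissection and excision, staining characteristics of each lymph node will be documented as blue, radioactive, or fluorescent", or a combination of these. Section 7.7 lists the same item under biopsy results, and the schedule in Appendix 4 puts it in the column for results as they become available. Section 8.1 also describes use in the patient, with "detection of nodes using the fluorescence PDE camera" in Cohort 1 and camera observation of lymphatic streams in Cohort 2. It does not ask for a record of which tracer led the surgeon to each node.

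The section 9.2.2 table sorts SLNs into five tracer categories: fluorescence only, radioisotope with or without fluorescence, and blue dye with or without fluorescence. A further row covers metastases. There is no row for nodes with no tracer or nodes taken by random sampling.

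Two further statements matter. Section 1 says of fluorescence that it "cannot be detected at a depth of more than 1cm with current technology". Appendix 1 says: "Where no SLNs are identified by the ICG the surgeon will randomly sample axillary nodes".

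**The concern.** Identification is something that happens in the axilla: either a tracer shows the surgeon a node or it does not. Fluorescence of a removed node shows that ICG reached it, which is a different fact. The two can differ because excision takes away the overlying tissue that may have hidden the signal.

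The difference matters most in the ICG-alone arm when ICG shows nothing and the surgeon samples at random. If a sampled node then fluoresces, the only tracer row open to it in section 9.2.2 is fluorescence only, the same entry as a true ICG success. If it does not fluoresce, it has no tracer row at all. The table therefore cannot display the failure that Appendix 1 anticipates.

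At stake is the identification rate of ICG as a sole tracer. Section 9.1 intends the pilot data to inform the clinically significant difference and the sample size of a larger trial. A later analysis plan can define success, but it cannot recover an intra-operative finding that was never written down.

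**Working it through.** The protocol states no figure that depends on this point, so there is none to reproduce. The sample size is a feasibility number; its only arithmetic, 4 groups × 25 = 100 (section 4), agrees.

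**Step 1: can the text lead to the misclassification?**

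1. ICG shows no SLN, and the surgeon samples axillary nodes at random (Appendix 1).
2. Tracer status is documented after excision (sections 8.1 and 7.7, Appendix 4).
3. A node hidden by depth in the patient can fluoresce once the tissue over it is gone (inferred from section 1).
4. In the ICG-alone arm such a node fits only the fluorescence-only row (section 9.2.2).
5. No passage says that step 1 makes the patient a failure whatever is seen later.

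The route is open, although the text does not require it to be taken.

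**Step 2: how large could the effect be in the ICG-alone arm?**

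Inputs: n = 25 per arm (section 4), with each cohort analysed separately (section 9.2.2). Section 1 gives ICG-alone identification rates above 90% in early studies and 98.7% in a Japanese comparison. I treat these as true in-patient rates *p*, which is an assumption, and add 95% as an assumed middle value. The share *f* of ICG failures later scored as fluorescent is not in the documents, so I assume 0 to 1.

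Formulas: expected failures = 25 × (1 − p); chance of at least one failure = 1 − p^25; recorded rate = p + (1 − p) × f.

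| p | Expected failures in 25 | Chance of ≥ 1 | Recorded, f = 0 | f = 0.5 | f = 1 |
|---|---|---|---|---|---|
| 90% | 2.5 | 93% | 90% | 95% | 100% |
| 95% | 1.25 | 72% | 95% | 97.5% | 100% |
| 98.7% | 0.3 | 28% | 98.7% | 99.4% | 100% |

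Example for p = 90%, f = 0.5: 0.90 + 0.10 × 0.5 = 0.95. Because section 1 says above 90%, 2.5 failures is an upper limit on that basis.

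In whole patients, one reclassification moves the rate by 1/25 = 4 percentage points. Exact (Clopper-Pearson) 95% intervals:

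- two failures: 23/25 = 92% (74.0 to 99.0)
- one of them recredited: 24/25 = 96% (79.7 to 99.9)
- both recredited: 25/25 = 100% (86.3 to 100)

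**Step 3: what happens in the combination arms?**

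There the outcome is identification with ICG combined with a standard tracer. A node found by gamma probe or blue colour is already a success. If it also fluoresces after removal, it moves from the radioisotope-only or blue-only row to the corresponding row with fluorescence. That raises apparent ICG concordance within the arm. It leaves the arm's identification rate, and hence the randomised comparison, unchanged.

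**The case against.** The strongest reply is that the protocol already treats identification as intra-operative. Section 3.6 times it at biopsy. Appendix 1 makes ICG failure a judgement reached before any sampling, and it speaks of axillary nodes, whereas the section 9.2.2 table counts SLNs. On that reading the patient is already a failure. The wording of section 8.1 fixes when status is written down; it does not say that fluorescence is judged only on the removed node. This stands as far as it goes: the misclassification is a possibility left open, not an instruction. But nothing in the protocol records the intra-operative judgement or says that it prevails.

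Second, the depth limit is less severe than it sounds. Section 1 explains that channels, if not seen through the skin, "can otherwise only be detected (together with sentinel nodes) after the skin incision has been made". Dissection itself reduces depth, and section 2 describes real-time dissection guided by fluorescence. This stands too. Most nodes may truly be found by ICG, so a reader should not infer that ICG cannot find deep nodes in the patient.

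Third, a reader might infer that the error always favours ICG alone. The documents do not support that for the comparison. If both tracers failed in a combination arm and sampling followed, a sampled node that fluoresced would be credited to that arm in the same way.

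Fourth, the CRF and the analysis plan are not shown and may cover this. Section 8.5 does place use of tracers in the CRF, but under treatment compliance and without saying which tracer located which node. Sections 7.6 and 10.1 limit data collection to what the protocol's outcomes and aims, and participants' eligibility and safety, require, so the protocol is the right place to name the item.

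Finally, this is an exploratory pilot, and a 4-point shift is small beside an interval of 74.0 to 99.0%. That limits the consequence. The information is nevertheless available in theatre at almost no cost.

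**Conclusion.** The point holds as a gap in data collection and endpoint definition. As written, the protocol allows an ICG failure followed by random sampling to be counted as a success, and its table cannot show such a failure. The exposure is in the ICG-alone identification rate: one patient is worth 4 points in an arm of 25, and a true 90% could be recorded as anything from 90 to 100%. That range rests on an assumed recredited share of 0 to 100%, so it includes no bias at all; the documents give no basis for narrowing it. It also assumes that the rates cited in section 1 reflect in-patient detection.

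The documents do not show that inflation will occur, and they do not fix its direction for the between-arm comparison. Nodes found by probe or blue dye in the combination arms affect only the concordance figures within those arms. The change is worth making before recruitment because an in-situ finding that is not recorded cannot be recovered afterwards.

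**What to change.** - **Section 8.1 and the theatre CRF:** for each node, record how it was first located in situ (fluorescence, gamma probe, blue colour, palpation or random sampling), as an item separate from its tracer status after excision.
- **Section 9.2.2 table:** add a row for no tracer or random sampling.
- **Section 3.6:** define success by the same rule in both arms, as at least one node located in situ by an allocated tracer before any random sampling. A patient with none counts as a failure whatever fluorescence is seen after excision. A strict rule for the ICG-alone arm only would itself bias the comparison against the intervention.
- **Ex vivo status:** use it for the concordance table only.

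The cost is one extra CRF item per node, a few sentences of protocol text and possibly a slightly lower reported identification rate. No surgical procedure or clinical rule changes.
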